Sequence and Timing of visits: Each subject will undergo up 2 visits to the lab. One sleep study will be conducted while wearing CPAP for the entire night. The second sleep study will be conducted using nasal dilator strips (NDS) as a placebo, instead of wearing CPAP, the entire night. NDS have been used in other studies as a CPAP placebo and have no impact on OSA severity [6]. The studies will be performed in random order, occurring >1 week apart and no longer than 3 months apart. To maximize chances of eliciting OSA during the non-CPAP study night, patients will be asked to refrain from CPAP use, for two nights preceding their non-CPAP study night. They will be provided with ClearPassage® NDS to use at home during CPAP withdrawal nights. This will ensure CPAP “washout” since therapeutic carryover effects of CPAP have been observed in some studies[7]. Patients who were previously enrolled in the single-night study (within-night CPAP withdrawal) will be invited to return for these additional sleep studies.

Study eligibility: To be enrolled in the study, participants will need to undergo a screening questionnaire and meet inclusion/exclusion criteria. They will need to provide written consent for participation. To avoid issues of CPAP intolerance, participants must also be accustomed to using CPAP, and report that they are capable of sleeping with CPAP on.

As of March 16, 2020 (or approval of this eFormA update), and in order to mitigate risks related to COVID-19 exposure to participants and study team, phone screening procedures will be completed from the study team members' home using a connecting service, such as Google Voice or Skype Voice-to-IP to protect study team members' personal contact information while allowing them to continue job functions from a safe location. Participants will be notified of the change in procedure.

Consent: In order to minimize the need for research-only in-person visits, telemedicine visits may be substituted for in person clinical trial visits or portions of clinical trial visits where determined to be appropriate and where determined by the investigator not to increase the participants' risks. Prior to initiating telemedicine for study visits

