the study team will explain to the participant, what a telemedicine visit entails and confirm that the study participant is in agreement and able to proceed with this method. Telemedicine acknowledgement will be obtained in accordance with the Guidance for Use of Telemedicine in Research. In the event telemedicine is not deemed feasible, the study visit will proceed as an in-person visit. Telemedicine visits will be conducted using HIPAA compliant method approved by the Health System and within licensing restrictions. Potential subjects will be provided with a copy of the Informed Consent form prior to the remote consent meeting either via email, fax, mail or previously provided during an in person visit. Potential subjects will then be contacted by phone by a consent designee to review the consent form in detail. Potential subjects will be given adequate time to consider the research study and ask questions prior to signing the consent form. The potential subject will then sign and date/time the informed consent document and it will be mailed, emailed or faxed to the consent designee, who will also sign/date/time. A copy of the fully signed CF will be returned to the volunteer.

Covid-19 screening: Participants will be asked screening questions on the phone for Covid-19 symptoms and risk exposure at the time they are given an appointment and 24-48 hours prior to each study visit. If they screen positive, they will not be eligible to participate until they are deemed safe to return to work by CDC criteria.

Covid-19 testing: Prior to each sleep study at the CRU, Covid-19 testing will be performed within 72 hours of the admission. A negative result will be required for the participation. If the participants claim to have been tested, they will be asked to provide a written proof of such test with a negative result within 72 hours of the admission.

Standard Precautions to be followed by subjects and staff to minimize the risk of coronavirus transmission:

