Subjects will be instructed to follow the visitor policy during each study visit. They will be given an Information Sheet about COVID-19 Related Risks through email prior to the visit. They will be instructed to come alone to the CRU, wear a face mask upon entry to the building, practice social distancing and hand hygiene. Study team will minimize face-to-face contact with the participants using all remote means possible during study visits. They will adhere to 6-foot distance between participants and staff or between staff and other staff whenever feasible. Staff will be trained to use a surgical or procedure mask with a face shield PPE at a minimum for all participant interaction. During a CPAP sleep study, Airborne and Contact Precautions with Eye Protection PPE will be used (isolation gown, double exam gloves, N95/Drager respirator with a face shield). The door of the patient room will be kept closed whenever possible during a CPAP sleep study.

Pre-sleep procedures. Subjects will undergo a brief history and physical examination. They will report to the clinical research unit and undergo anthropometric assessment including weight, height, neck, and waist circumference. A point of care screening test for hemoglobin will also be performed to exclude pre-existing anemia. Patients with a hemoglobin < 10 g/dL are ineligible for this study. At approximately 17:30, they will eat a standard dinner containing 30% fat, 50% carbohydrate, and 20% protein with kcal based upon the Mifflin-St Jeor formula. Two peripheral IV's will be placed for blood sampling during sleep, with one as a backup in case of failure of one IV. IV tubing will be extended to an adjacent control room so that blood samples can be obtained without disturbing the subject.

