PSG setup. On each study night from 22:40 until 06:40, a PSG will be performed. The sleep study will include electroencephalography, electrooculography, oxygenation, respiratory effort, CPAP airflow, and transcutaneous CO₂ monitoring. Respiratory effort will be measured by thoraco-abdominal movement assessed by mercury strain gauges. Surface electrodes will be placed at C₃A₂ and C₃O₁, a submental electrode, and left and right electro-oculogram will be used to stage sleep. Electrocardiograph (EKG) tracings will be recorded from three chest electrodes. Continuous measurement of oxygen saturation will be recorded using an ear oximeter (model No 472-1A, Hewlett Packard, Waltham, Mass). Transcutaneous CO₂ will be monitored using a Radiometer TCM-4 device. Signals from the electroencephalograph, EKG, electromyogram, electrooculogram, respiratory strain gauge, ear oximeter and thermistors will be recorded on a computer with RemLogic software.

During the CPAP night, patients will sleep using CPAP set to their prescribed home CPAP settings. Airflow will be recorded with a pneumotachograph in the CPAP circuit. CPAP pressure will be titrated if necessary to prevent

obstructive hypopneas and apneas. During NDS nights, ClearPassage® strips will be applied at bedtime. Flow will be measured using a nasal cannula and oral thermistor.

[figure not shown]
Blood work and urine collection

All samples will be obtained via the indwelling IV, without awakening the subject. Blood samples will be drawn at 30 to 60 minute intervals beginning at 5:30 PM and continuing until the next morning at 6:30 AM as shown in the figure below. At 10:30 PM, when the sleep study starts, blood is sampled at 30 minute intervals in order to capture dynamic changes in FFA metabolism during sleep. Each blood sample will be 4 cc in volume and placed into lavender top tubes (EDTA) for centrifugation to obtain plasma. Cells are removed from plasma by centrifugation for 10 minutes at 1500 x using a refrigerated centrifuge. If necessary, based on nursing schedules, the timing of sampling and sleep procedures can be shifted up to 1 hour later or earlier.

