Dual-energy X-ray absorptiometry (DEXA). After the baseline glucose level for the OGTT has been drawn and the patient has consumed the glucose solution, they will undergo a DEXA scan. The DEXA scan will be used to estimate fat mass, which will be one of the variables analyzed as a predictor of FFA elevation.

Subjects may eat breakfast after the OGTT testing is completed

To minimize the impact of sleep loss on driving safety, subjects are asked to either (1) arrange for an alternate means of transportation home (this is mentioned on the consent or to (2) sleep as needed for up to 4 additional hours before discharge.

Repeat sleep testing:

Repeat sleep tests may be requested from the subject under the following circumstances:

- (1) A technical problem with data acquisition including PSG lead failure/artifacts, incomplete blood collection from IV insertion or maintenance problems.
- (2) Poor sleep efficiency <50% of time in bed

If the initial sleep study meets these criteria and a repeat test is deemed necessary by the PI, then the repeat testing will be scheduled at least 1 week following the initial study.

Scoring. Sleep will be scored according to Rechtschaffen and Kales criteria. Respiratory events will be scored according to AASM criteria. Apneas will be considered present when there is no air flow for >10 seconds. Obstructive apneas will be considered present when apneas are associated with positive strain gauge deflections indicating thoracic movement. Apneas will be considered central in origin when cessation of air flow is not accompanied by thoracic movement as measured by the strain gauge. Mixed apneas will be defined by episodes of no air movement resulting from central apnea followed by obstruction. Hypopneas will be scored for reductions in airflow of 30% lasting >10 seconds accompanied by either an arousal or fall in oxyhemoglobin saturation of 3% or greater.

Data Analysis and Anticipated Outcomes:

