Nasal dilator strips: These are non-latex, adhesive tape applied to the nose designed to mitigate snoring and nasal congestion. There may be discomfort using NDS, and they are inferior to CPAP for treating OSA.

DEXA scan: DEXA scans are considered safe and deliver minimal radiation.

Oral glucose tolerance test: There are no significant risks to this standard clinical test other than the associated phlebotomy.

EndoPAT: There are no significant risks to this test other than arm discomfort during the procedure.

Confidentiality of genetic material: There is the risk that genetic data is revealed outside the study. Information can also lead to unwanted psychological or financial consequences if it were released to a third party.

b. Steps taken to minimize the risks.

Veni-Puncture: Discomfort, bruise formation, and infection will be minimized by use of sterile supplies and aseptic technique by trained personnel.

Phlebotomy: The volume of each blood draw is minimized to balance safety with the need to obtain a useful amount of plasma after centrifugation. The risk of inducing hemodynamic or cardiovascular stress is minimized by excluding those with significant baseline anemia (hemoglobin <10 mg/dl). Those found to have anemia will be informed of the results and advised to seek medical evaluation as appropriate.

Withdrawal of CPAP. Subjects will be advised to arrange transportation home so that they do not need to drive. They will be advised to increase their total sleep time, if necessary, during CPAP abstinence to minimize sleep deprivation off CPAP. On the day of the non-CPAP sleep study, if they plan to drive home themselves, they will be provided with an additional 3-4 hours of time in the lab to sleep before discharge. Participants with high-risk occupations requiring vigilance, such as commercial drivers and pilots, will be excluded. Participants who have ever been in a near-miss or motor vehicle accident due to sleepiness will be excluded. When communicating with patients about their off-CPAP visits, patients will be asked in the 1-2 days before their visit if they have experienced any near-miss events or motor vehicle accidents. If they have, then they will be excluded from the study, advised to resume CPAP immediately, and to avoid driving or other high risk activities until they have used CPAP for 3 nights.

DEXA scan: DEXA uses a beam of very low radiation, delivering <10% radiation as during a clinical chest X-ray.

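### The accident and near-miss question before the off-CPAP visit follows at most one of the two home nights off CPAP, and no repeat on arrival is specified

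*Combined protocol and SAP*

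**What the plan says.** Section 4a (Sequence and Timing of visits) sets the withdrawal schedule: "patients will be asked to refrain from CPAP use, for two nights preceding their non-CPAP study night". Section 4d gives the total as three nights, which includes the laboratory night on nasal dilator strips (NDS). Section 4c lets participants who have been unable to stop CPAP for that long stay on it until the laboratory study. Of the two visits, section 4a says: "The studies will be performed in random order, occurring >1 week apart and no longer than 3 months apart".

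Section 7a names sleepiness-related accidents, including road collisions, as a risk that withdrawal raises. Section 7b (Withdrawal of CPAP) responds with a specific check: in contacts about the off-CPAP visit, "patients will be asked in the 1-2 days before their visit if they have experienced any near-miss events or motor vehicle accidents". A participant who answers yes is excluded, told to go back on CPAP at once, and told not to drive or do other risky activities until CPAP has been used for three nights.

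On the day of the visit, section 4a (Pre-sleep procedures) provides: "Subjects will undergo a brief history and physical examination". It does not name the accident question. For the next morning, section 4a says: "To minimize the impact of sleep loss on driving safety, subjects are asked to either (1) arrange for an alternate means of transportation home". The alternative is to sleep in the laboratory before leaving, for up to 4 hours in section 4a and 3 to 4 hours in section 7b.

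**The concern.** The rule in section 7b is meant to stop someone who has just had a driving event from staying off CPAP and continuing to drive. It works only if the event is known. The plan times the question to the day or two before the visit, while withdrawal at home is still under way. The second home night, and the driving on the day of the visit, normally come after it.

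A near-miss late on the day before the visit, or on the way to the unit, may then go unasked. The participant would have one more night off CPAP and could leave by car after some extra sleep, which the rule would have forbidden. What is at stake is participant safety. The sample size, the estimand and the analysis are not affected.

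**Working it through.** **Inputs.** Two home nights off CPAP (section 4a); three off-CPAP nights in total (section 4d); question one to two days before the visit (section 7b); dinner at about 17:30 and polysomnography from 22:40 (section 4a); enrolment target 92 (Sample Size).

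**1. Reproduce the plan's total.** Call the visit day 0. The off-CPAP nights begin on the evenings of day -2 and day -1 (home) and day 0 (laboratory): 2 + 1 = 3, which agrees with section 4d.

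**2. Count the home nights completed when the question is asked.**

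| Question asked | Home nights off CPAP completed (of 2) |
|---|---|
| Day -2 | 0 |
| Day -1 | 1 |
| Day 0, on arrival | 2 |

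The denominator is two because the third night is the laboratory night itself. No question before that night can follow more than two.

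**3. Check by hours.** Counting back from 17:30 on day 0, 48 hours earlier falls before the first home night (0 completed) and 24 hours earlier falls between the two (1 completed). An earlier afternoon arrival gives the same counts. The COVID-19 symptom call has a similar window, "at the time they are given an appointment and 24-48 hours prior to each study visit", but the plan does not say that the accident question is asked in that call.

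**4. Follow one participant through the plan.** Suppose a near-miss occurs on day -1 after the question, or on day 0.

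- As written: nothing prompts disclosure at arrival. The NDS night goes ahead, and the participant may drive home on day 1 after extra laboratory sleep. CPAP nights between the event and that drive: 0. The rule requires 3.
- With a question on arrival and a yes: the NDS night is not run, CPAP resumes on the night of day 0, and the no-driving advice runs through the nights of days 0, 1 and 2.

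**5. Is there time to act?** From "At approximately 17:30, they will eat a standard dinner" to the start of recording ("On each study night from 22:40 until 06:40, a PSG will be performed") is 22:40 - 17:30 = 5 h 10 min. Section 4a allows procedures to move by up to an hour. If the sleep study alone moved an hour earlier, 4 h 10 min would remain.

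**6. Events missed.** The documents give no accident or near-miss rate under withdrawal, so no number of missed events can be derived.

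**The case against.** The strongest reply is that the wording does not force the count. A window leading up to a late-afternoon visit could include the morning of day 0, after both home nights. The one to two days might even be the period asked about and not the time of asking. Neither reading is impossible. The word order ties the timing to the asking, however, and on any reading no question at arrival is stated.

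The second reply is that other safeguards exist, and they do. Section 7b excludes anyone who has ever had a sleepiness-related near-miss or accident, without a cut-off date, so an event volunteered on arrival would already justify exclusion. The same section excludes high-risk occupations and advises longer sleep. Section 4f removes those who cannot tolerate being off CPAP. Section 7c monitors adverse events throughout, and the history on arrival could bring an event to light. What these leave open is narrow: none prompts the question at arrival or attaches the return to CPAP and the driving ban to it. A near-miss without injury also need not count as a severe event under section 7c, so the Early stopping rule may not apply.

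The third reply is that a question at arrival cannot undo driving already done. That stands, and it limits the gain. A reader might infer that most waking time off CPAP goes unscreened and that the repeat would protect it. The documents do not support that: the time has passed by arrival, the hour of arrival is not stated, and the hour of the question is not fixed. Nor should the finding be expressed as coverage of one night in three, because the third night follows any question asked before it.

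**Conclusion.** The point holds in a limited form. On the standard schedule and the calendar-day reading, the question follows none or one of the two home nights, against both if it were also asked on arrival. An event later on day -1 or on day 0 may therefore fail to trigger the plan's own rule.

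The gain from closing the gap is modest. It covers one supervised laboratory night, a trip home that already has safeguards, and driving advice for the following days. It does nothing for driving before arrival, and it does not apply to participants who keep CPAP until the laboratory night. Those who have the NDS night first have a later scheduled contact, but that is more than a week away.

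The conclusion assumes that staff follow the text and do not already ask at arrival. If they do, the change only records the practice. A reader might infer that the plan leaves withdrawal accidents unmonitored, and it does not: it has an active question, a firm rule and several supporting measures. This is a cheap improvement to a rule already in place.

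**What to change.** Add one sentence to section 7b: keep the pre-visit question, ask it again on arrival for the NDS night (including any repeat NDS night) before the sleep study starts, and apply the same rule. If the answer is yes, do not run the NDS night, have the participant resume CPAP that night, and arrange travel home that does not require them to drive. Asking once more before discharge is optional and would serve to prompt driving advice.

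Cost: at an assumed 1 minute per NDS visit, 92 × 1 = 92 minutes, about 1.5 hours of staff time over the whole study; at 3 minutes, 92 × 3 = 276 minutes, or 4.6 hours. Any repeat NDS night adds one more asking. The other downside is possibly a few late exclusions, each after an admission slot has been booked. These are exclusions that the plan's rule already intends.

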Study-related assessments will not be charged to the subject. Parking fees will be paid. Subjects will be responsible for any treatment of conditions that are uncovered as part of the study evaluations or if they are injured as a result of being in the study.

8. Benefits

a. Description of the probable benefits for the participant and for society.

There are no direct benefits to participants for being in this study. This study will help researchers learn whether OSA causes nocturnal FFA elevations and whether CPAP is effective in preventing the elevations.

9. Payment and Remuneration

a. Detail compensation for participants including possible total compensation, proposed bonus, and any proposed reductions or penalties for not completing the protocol.

Participants will be paid up to \$600 for completing all parts of this study, based on the following procedures:

- \$200 for each sleep study (2 visits)
- \$25 for each oral glucose tolerance test and EndoPAT test (done after each of the 2 visits)
- \$50 for a DEXA scan (only done once)
- \$100 study completion bonus for participants who are able to keep their appointments as originally scheduled. They will forfeit this bonus if they must reschedule their visit(s).
- They will also receive parking reimbursement so there is no fee to come to our laboratory.

10. Costs

a. Detail costs of study procedure(s) or drug (s) or substance(s) to participants and identify who will pay for them.

Participants will not be billed for study procedures. Polysomnograms and blood tests will be billed to the study at standard CRU rates

Reference List

1. Jun, J.C., et al., *Effects of sleep apnea on nocturnal free fatty acids in subjects with heart failure*. *Sleep*, 2011. **34**(9): p. 1207-1213.
2. Schaffer, J.E., *Lipotoxicity: when tissues overeat*. *Curr.Opin.Lipidol.*, 2003. **14**(3): p. 281-287.
3. Young, T., et al., *The occurrence of sleep-disordered breathing among middle-aged adults*. *N Engl J Med*, 1993. **328**(17): p. 1230-1235.
4. Jun, J. and V.Y. Polotsky, *Metabolic consequences of sleep-disordered breathing*. *ILAR J*, 2009. **50**(3): p. 289-306.
5. Punjabi, N.M., et al., *Sleep-disordered breathing and mortality: a prospective cohort study*. *PLoS Med*, 2009. **6**(8): p. e1000132.
6. Amaro, A.C., et al., *The use of nasal dilator strips as a placebo for trials evaluating continuous positive airway pressure*. *Clinics (Sao Paulo)*, 2012. **67**(5): p. 469-74.

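### The $100 completion bonus is lost on any required rescheduling, with no exception for a deferral the study itself imposes, so an honest answer to the Covid-19 screen costs the participant money

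*Combined protocol and SAP*

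**What the plan says.** Section 9 (Payment and Remuneration) lists the payments and makes $100 of the total depend on attending on the dates first booked. The condition reads: "They will forfeit this bonus if they must reschedule their visit(s". No reason for rescheduling is exempted.

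Section 4a (Covid-19 screening) asks about symptoms and exposure by phone when the appointment is given and again 24 to 48 hours before each visit. On a positive screen: "If they screen positive, they will not be eligible to participate until they are deemed safe to return to work by CDC criteria". The next paragraph (Covid-19 testing) also requires a negative test within 72 hours of each admission.

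Section 7b (Withdrawal of CPAP) contains a second self-report check, tied to the off-CPAP visits: "patients will be asked in the 1-2 days before their visit if they have experienced any near-miss events or motor vehicle accidents". Anyone who reports such an event is taken out of the study.

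On travel, section 7b says: "Subjects will be advised to arrange transportation home so that they do not need to drive". The only travel cost that section 9 covers is parking: "They will also receive parking reimbursement so there is no fee to come to our laboratory". Section 7e likewise mentions only parking fees.

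**The concern.** Both checks depend on what the participant chooses to disclose, and in both cases disclosure costs money. For the Covid-19 screen the link is direct: a positive answer shortly before the visit leads to deferral, deferral means a new date, and a new date forfeits the bonus. The participant has done nothing except answer truthfully. The same loss follows a positive test, which is not under the participant's control.

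What is at stake is participant and staff safety and the fairness of the payment terms. No endpoint, sample size or analysis depends on it.

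The travel terms raise a smaller issue of the same kind. The plan advises against driving home after the off-CPAP night, yet the only travel support listed in section 9 goes to people who come by car.

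**Working it through.** **Inputs (all from section 9).** $200 per sleep study, two visits; $25 per visit for the morning tests; $50 for one DEXA scan; $100 bonus; stated maximum $600.

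**Step 1: reproduce the stated maximum.** The morning-test item, in dollars, reads "25 for each oral glucose tolerance test and EndoPAT test (done after each of the 2 visits". Taken as one payment per visit for the pair of tests:

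2 × 200 + 2 × 25 + 50 + 100 = 400 + 50 + 50 + 100 = $600.

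This matches. Taken as $25 for each test separately, the total is 400 + 100 + 50 + 100 = $650, which does not match. The first reading is used below.

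**Step 2: cost of a truthful positive Covid-19 screen after booking.** The visit moves, the bonus is lost, and everything else can still be earned:

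- Maximum still available: 600 − 100 = $500.
- Share lost: 100 / 600 = 16.7%.

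A positive answer at the booking call comes before any appointment exists, so only the screen 24 to 48 hours before the visit triggers the loss.

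**Step 3: cost of a reported near-miss or accident.** Here the participant is excluded, not rescheduled. Section 9 does not say how exclusion affects payment. I assume payment per completed procedure and no completion bonus. Visit order is random (section 4a), so the off-CPAP night may come first or second.

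| Off-CPAP visit is | Already earned | Lost | Lost if the bonus were kept |
|---|---|---|---|
| Second, DEXA done | 200 + 25 + 50 = $275 | 600 − 275 = $325 | $225 |
| Second, DEXA not done | 200 + 25 = $225 | 600 − 225 = $375 | $275 |
| First | $0 | $600 | $500 |

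The rescheduling clause plays no part in these losses. Protecting the bonus returns $100 of a loss between $325 and $600; the rest is payment for procedures that were not done.

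**Step 4: travel.** Section 9 lists reimbursed parking and no payment for a ride. The documents give no fares, so the difference cannot be put in dollars.

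**The case against.** The strongest case on the other side has five parts.

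- **The clause may be meant only for changes the participant asks for.** The participant is its grammatical subject, so this is possible. But the wording is about having to reschedule, which naturally includes involuntary changes, and the form's own prompt asks for reductions and penalties to be detailed there. If the narrower meaning is intended, one sentence settles it.
- **The self-report checks do not stand alone.** A reader might infer that they are the only protection against infection or against accidents off CPAP. The documents do not support that. For Covid-19 there is the mandatory negative test, with masks, distancing and protective equipment (section 4a). For CPAP withdrawal there are exclusions for prior drowsy driving and for high-risk occupations (sections 5 and 7b), advice to extend sleep, and sleep time in the lab before discharge for those who drive. This limits the harm from a concealed answer. It does not remove the penalty on an honest one, and the plan describes no objective check behind the near-miss question.
- **The near-miss loss is ordinary payment per procedure.** This stands. The bonus is the only part that a change to the clause can address.
- **Near-misses are not an outcome.** A reader might infer that under-reporting would bias the study's main safety information on withdrawal. No section gives near-miss reports that role. In section 7b the question is an exclusion check, safety data come from adverse-event monitoring throughout the study (section 7c), and no planned analysis uses near-misses.
- **Rides may be covered elsewhere.** Section 4a notes that the consent form mentions alternate transport, and the consent pages are not available here. Section 4a also accepts sleeping before discharge as an alternative to arranging transport. The travel point is therefore secondary, and that reimbursed parking leads anyone to drive is inference only.

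It is also not shown that the clause reaches repeat studies after IV or recording failures (section 4a, Repeat sleep testing). Those are extra tests requested after an attended visit.

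**Conclusion.** The point holds for the Covid-19 screen. Read as written, sections 4a and 9 together take $100, or 16.7% of the maximum payment, from a participant who truthfully screens positive 24 to 48 hours before a visit. This rests on two assumptions: that the clause is applied literally, and that no exception appears in the consent form.

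For the near-miss question the financial disincentive is larger, $325 to $600 under the payment assumption stated above, but it arises from exclusion. Only $100 of it is open to correction through the bonus.

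The travel mismatch is real within section 9 but may be resolved in the consent form. The documents contain no evidence that any participant has concealed an answer or driven because of these terms. The finding concerns the direction of the incentive. The repair is small and worth making, and it leaves the design and analysis untouched.

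**What to change.** In section 9, state that the bonus is kept when a visit is postponed or stopped because of illness, a Covid-19 screen or test result, a reported near-miss or accident, or a reason initiated by the study, and that it is forfeited only when a visit is rescheduled for the participant's convenience. The phrase covering study-initiated reasons also settles how repeat studies are treated. The deferral and exclusion rules themselves need no change for this purpose.

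Secondary: let the travel reimbursement for the off-CPAP visit be used for a ride home instead of parking, and make section 9 agree with the consent form on transport.

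Cost: an IRB amendment to the payment text, at most $100 per affected participant, and any difference between a fare and parking. The bonus is already inside the $600 maximum, so keeping it never raises the most that one participant can be paid. Even if all 92 planned participants were affected, the bonus cost would be 92 × 100 = $9,200, the same sum that would be due if everyone attended as first booked.
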